1.2 SCHEMA

All subjects will receive fostamatinib 100 mg BID for 4 weeks. On the 4-week evaluation,

- a) if the cytopenia/s improves (hemoglobin ≥10 g/dL and/or platelets ≥ 50 x 10⁹/L), patients will continue the same dose for a total of 12 weeks; b) if refractory cytopenias persist (hemoglobin < 10 g/dL, platelets < 50 x 10⁹/L), pts will increase dose to 150 mg BID.

* Subjects with persistent (≥2 readings, 2 weeks apart) loss of hematologic response after week 5 can increase dose to 150mg BID until end of the study on week 12.

*Temporary drug interruption: Patient to receive total of 12 weeks of fostamatinib despite drug interruptions. If patient have drug interruptions, patient will be maintained in protocol until finishing the total 12 weeks of the treatment.

Abbreviated Title: Fostamatinib for post-transplant cytopenias
Version Date: 11/28/2023

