	
by week 12, compared to the week prior to the start of the study drug.
 
 3. Change in corticosteroid dose over time, measured by median daily weight-based prednisone-equivalent corticosteroid dose in a week, from week 1 to week 12 4. Change in other immunosuppressant dose over time, measured by median daily dose of the immunosuppressant in a week, from week 1 to week 12 5. Number of patients who achieved $\geq 50\%$ steroid dose reduction by week 12 compared to week 1 6. Incidence and severity of cGVHD according to 2014 NIH Consensus Criteria, at baseline before the initiation of treatment, and at week 12 	
Tertiary/Exploratory		
The exploratory objective is to evaluate changes in serologic marker while on treatment to identify key biological pathways impacted by fostamatinib that may lead to a response to therapy	
 1. Absolute percentage change in B cell chimerism pre-treatment, vs weeks 4 and 12. 2. cPRA change in the preformed HLA antibodies before and after treatment in subjects with thrombocytopenia or Evans syndrome 3. Percent MFI change of preformed HLA antibodies before and after treatment. This applies for antibodies with an MFI $>1,000$. 4. Anti-RBC alloantibody titer change in patients with hemolytic anemia before and after treatment 5. Assessment of serial cytokines pre-treatment and weeks 4 and 12. Cytokines include CRP, IL-1, IL-2, IL-6, IFNγ, TNFα, EPO and TPO 6. Immunoglobulin level changes pre-treatment, and weeks 4 and 12. 	These exploratory endpoints are relevant to the ex vivo and in vitro analysis that will help predict response and define mechanisms of action of fostamatinib for resolving cytopenias

	
7. Absolute reticulocyte count, lactate dehydrogenase, haptoglobin changes pre-treatment, and at each biweekly study visit, in patients with anemia or Evans syndrome
 
8. Change in the weekly rate and severity of bleeding according to the total score of the IBLS, from week -1 (one week before the start of the study drug) to week 12, in subjects with thrombocytopenia or Evans syndrome[#]
	
--	--	--

&: Baseline is defined as the mean of the last two hemoglobin or platelet measured at least 24 hours apart, at least 72 hours from the last transfusion, within 14 days of the start of the study drug

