6.1.2.1 Dose Continuation or Dose Escalation

On the 4-week evaluation,

a) if cytopenia improves (hemoglobin \geq 10 g/dL, platelets \geq 50 x 10^9 /L), patients will continue the same dose for a total of 12 weeks,

b) if refractory cytopenias persist (hemoglobin $<$ 10 g/dL, platelets $<$ 50 x 10^9 /L), the dose will be increased to 150 mg BID. Subjects with persistent (\geq 2 readings, 2 weeks apart) loss of hematologic response after week 5 can increase their dose to 150 mg BID until at end of the study on week 12.

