6.1.2.3 Dose Modifications

Fostamatinib dose modification is recommended based on individual safety and tolerability. Management of some adverse reactions may require dose-interruption, reduction, or discontinuation.

A dose reduction schedule (DRS) is provided below. For example, if a patient is on the maximum (300mg total daily dose) at the time of an adverse reaction, the first dose reduction would be from 300mg/day to 200mg/day.

Dose Reduction Schedule (DRS)		
Total daily dose	Dosing Schedule	
	Morning	Evening
300mg	150mg	150mg
200mg	100mg	100mg
150mg	150mg ¹	---
100mg ²	100mg ¹	---

¹: Once daily fostamatinib should be taken in the morning.

²: If further dose reduction below 100mg/day is required, stop fostamatinib

Treatment may be delayed for a maximum of 14 days after holding the treatment for toxicities that develop and do not resolve as defined at 6.1.2.3 (neutropenia, LFT elevation, and diarrhea). The timing of subsequent lab and the study week are then adjusted to the study week that was stopped.

The recommended dose modification for adverse reactions are as the following:

	Recommended action
Hypertension Stage 1: systolic between 130-139 or diastolic between 80-89 mmHg	
 Initiate or increase dosage of antihypertensive medication for patients with increased cardiovascular risk, and adjust as needed until BP is controlled. If the BP target is not met after 8 weeks, reduce fostamatinib to next lower daily dose (refer to DRS). Consider cardiology consult

Stage 2: systolic at least 140 or diastolic at least 90 mmHg	
 Initiate or increase dosage of antihypertensive medication, and adjust as needed until BP is controlled. If BP remains 140/90 mmHg or higher for more than 8 weeks, reduce fostamatinib to next lower daily dose (refer to DRS). If BP remains 160/100 mmHg or higher for more than 4 weeks despite aggressive antihypertensive therapy, interrupt or discontinue fostamatinib. Consider cardiology consult

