Hypertensive crisis: systolic over 180 and or diastolic over 120 mmHg	
 Interrupt or discontinue fostamatinib. Initiate or increase dosage of antihypertensive medication, and adjust as needed until BP is controlled. If BP returns to less than the target BP, resume fostamatinib at same daily dose. If repeat BP is 160/100 mmHg or higher for more than 4 weeks despite aggressive antihypertensive treatment, discontinue fostamatinib. Consider cardiology consult
Hepatotoxicity	
AST/ALT abnormal at enrollment but < 3x ULN	Recheck LFTs every week to ensure it is still <3x ULN. Patient may have it checked locally and have results faxed to the NIH.
Increase in AST/ALT by x3 from level at the time of enrollment but less than 3 x ULN	
If patient is symptomatic (e.g., nausea, vomiting, abdominal pain):
 
 Interrupt fostamatinib. Recheck LFTs every 72 hours until ALT/AST values are no longer elevated (below 1.5 x ULN) and direct bilirubin (DBL) remains less than 2 x ULN. Resume fostamatinib at next lower daily dose (refer to DSR). 
If patient is asymptomatic:
 
 Recheck LFTs every 72 hours until ALT/AST are below 1.5 x ULN) and DBL remains less than 2 x ULN. Consider interruption or dose reduction of fostamatinib if ALT/AST and DBL remain in this category (AST/ALT is less than 3x ULN; and DBL remains less than 2 x ULN). If interrupted, resume fostamatinib at next lower daily dose (refer to DSR) when ALT/AST are no longer elevated (below 1.5 x ULN) and total BL remains less than 2 x ULN.

Abbreviated Title: Fostamatinib for post-transplant cytopenias

Version Date: 11/28/2023

Increase in AST/ALT by x3 ULN and DBL is less than 2 x ULN	
Interrupt fostamatinib. Recheck LFTs every 72 hours:
 
 • If AST and ALT decrease, recheck until ALT and AST are no longer elevated (below 3 x ULN) and total BL remains less than 2 x ULN; resume fostamatinib at next lower daily dose (refer to DSR). Per PI discretion, subject can be re-escalated one level at a time until back to the maximum tolerable dose • If AST/ALT persist at 5 x ULN or higher for 2 weeks or more, discontinue fostamatinib.
AST/ALT is 3 x ULN or higher and DBL is greater than 2 x ULN	Discontinue fostamatinib

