- In the event that the subject is unable to tolerate 100 mg BID, the dose can be reduced to 150mg daily with re-assessment. If intolerable AEs with 150 mg daily, dose can be reduced to 100 mg daily. If unable to tolerate 100mg daily, patient will stop fostamatinib and will be off study. Intolerance is considered as any grade 3-4 AEs, probably or definitely related to fostamatinib, or any grade AE which, at the PI's discretion, appears to be distressing enough to the patient to lead to the drug's discontinuation. If the adverse events resolved and subject tolerates the dose reduction with no recurrence of AE, per PI discretion subject can be re-escalated one level at a time until back to the maximum tolerable dose.
- Causes of neutropenia in a AHCT recipient may include: infections such as cytomegalovirus infection, medication such as ganciclovir or other antibiotics, immunosuppressants such as mycophenolate or ruxolitinib, graft failure, relapse of primary disease. If neutropenia occurs, we will perform an extensively work up on the patient for the other causes stated above, and/or hold other potential culprit medications. We will give filgrastim to patients while doing the above work up. If no other causes are found, and the neutropenia does not recover, or recurs, with holding other medications, we will conclude that fostamatinib is contributing to the development of neutropenia.
- GvHD may mimic adverse events. If holding fostamatinib according to the DSR does not reverse the diarrhea, abdominal pain, transaminase elevation, AND there are no other causes (such as infection) identified, we will consider the cause of the adverse events to possibly be related to GVHD. In such circumstances, we will make every effort possible to perform biopsies of the involved organ systems to confirm the diagnosis of GvHD.

Dose adjustment for platelet counts and hemoglobin are as the following:

Thrombocytosis	
PLT $\geq 200 \times 10^9 /L$ to $\leq 400 \times 10^9 /L$ at any time	
 • Decrease the dose to the next lower dose level. Wait 2 weeks to assess the effects of this and any subsequent dose adjustments.
PLT $> 400 \times 10^9 /L$ at any time	
 • Stop fostamatinib. Increase the frequency of platelet monitoring to twice weekly. • Once the platelet count is $< 150 \times 10^9 /L$, resume fostamatinib at the next lower dose level

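### The platelet and hemoglobin dose rows in section 6.1.2.3 act on absolute counts, with no baseline or lineage limit, so a single-lineage subject can be stepped down or stopped for a count that was never low

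*Combined protocol and SAP*

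**What the plan says.** The count table in section 6.1.2.3 (Thrombocytosis and Polycythemia) has three tiers for each lineage:

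- **Step-down.** Platelets 200–400 × 10⁹/L, or hemoglobin 13–15 g/dL, whenever observed: "Decrease the dose to the next lower dose level. Wait 2 weeks to assess the effects of this and any subsequent dose adjustments".
- **Stop.** Platelets above 400, or hemoglobin above 15, whenever observed. Once platelets are below 150 or hemoglobin is below 13, the site is to "resume fostamatinib at the next lower dose level".
- **Discontinue.** Platelets above 400, or hemoglobin above 15, after 2 weeks at the lowest dose.

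The sentence introducing the table and the rows themselves mention neither baseline nor enrolled lineage. The Dose Reduction Schedule runs 300, 200, 150, 100 mg/day, and its footnote adds: "If further dose reduction below 100mg/day is required, stop fostamatinib". The section opens by describing dose modification as recommended and based on individual safety and tolerability.

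Sections 1.1 and 5.1 admit subjects with anemia, thrombocytopenia or both. Sections 5.1 and 5.2 set no upper limit on either count. Section 4 already defines a reference value for both lineages: "Baseline is defined as the mean of the last two hemoglobin or platelet measured at least 24 hours apart". Under section 6.1.2.1, for cytopenias still refractory at week 4, "the dose will be increased to 150 mg BID".

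**The concern.** The rows appear written for a count that started low and rose too far on drug. In a single-lineage subject the other count may be normal from the start. An anemia-only subject with platelets of 250, or a thrombocytopenia-only subject with hemoglobin of 13.5, then satisfies a step-down row before the drug has done anything. If that count is above 400 or 15, the text tells the site to stop and wait for a healthy lineage to fall below 150 or 13.

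Followed as written, this under-doses or withholds drug from eligible subjects for a reason unrelated to their disease or to toxicity. Enrollment is at the NIH Clinical Center and up to three further sites, so sites may also handle the rows differently. The trial treats 20 evaluable subjects and needs more than 4 responses, so avoidable under-dosing of a few subjects would count against the drug.

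**Working it through.** **The plan's own figure.** The plan states no number for these rows. The design they sit in (section 9.1: 11 then 9 subjects, continue with 2 or more responses, reject with more than 4 of 20) was checked as background. With Bin(n, p) a binomial count,

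P(reject) = Σ over x = 2 to 11 of P(Bin(11, p) = x) × P(Bin(9, p) ≥ 5 − x).

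At p = 0.35 this is 0.8600, matching the stated 86%. At p = 0.10 it is 0.0397, within the stated 0.05. Neither figure is in dispute.

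**Does the trigger apply to a never-low count?** Take an anemia-only subject with platelets of 250. Section 5.1 admits the subject, and 5.1 and 5.2 set no ceiling on platelets. In 6.1.2.3, 250 lies in the 200–400 row, and nothing requires a rise or an enrolled lineage. So the row applies. The same holds for a thrombocytopenia-only subject with hemoglobin of 13.5 and the 13–15 row.

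**What dose results?** Inputs:

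- dose levels from the Dose Reduction Schedule: 200, 150 and 100 mg/day;
- a 2-week wait between steps, from the step-down row;
- a CBC every 2 weeks, from section 1.3;
- 84 days of treatment.

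Assumptions: an anemia-only subject starts at the routine 100 mg BID, and platelets stay at 200–400 throughout.

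Planned dose:

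- escalated at week 4: 200 × 28 + 300 × 56 = 22,400 mg;
- not escalated: 200 × 84 = 16,800 mg.

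| Path | Arithmetic | Dose | % of 22,400 | % of 16,800 |
|---|---|---|---|---|
| One step at week 2, then held at 150 mg/day | 200×14 + 150×70 | 13,300 mg | 59% | 79% |
| Repeated steps from week 2, held at 100 mg/day | 200×14 + 150×14 + 100×56 | 10,500 mg | 47% | 62.5% |
| Repeated steps from Day 1, held at 100 mg/day | 150×14 + 100×70 | 9,100 mg | 41% | 54% |

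The re-escalation paragraph in 6.1.2.3 covers resolved adverse events. It gives no route back up after a count-driven reduction, so these paths assume none.

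**What happens above the stop limit?** For an anemia-only subject who enters with platelets above 400, the stop row is met at the first reading. Restart requires a count below 150, a level that a never-low lineage may not reach. Section 1.2 says "Patient to receive total of 12 weeks of fostamatinib despite drug interruptions", so a hold can be made up later, but only if the count falls.

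**The case against.** **Discretion.** Modification is recommended on the basis of individual safety and tolerability. The headings name abnormally high counts, and waiting to assess effects presupposes a response to drug. A sensible investigator may leave an unchanged normal count alone, and a Day 1 step-down is the least likely application. This stands as a reason to expect less harm in practice. It does not limit the rows, whose actions are imperative.

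**Lowest dose.** A reader might infer from the schedule's footnote that repeated step-downs end in a stop below 100 mg/day. The totals would then be 200×14 + 150×14 + 100×14 = 6,300 mg, or 150×14 + 100×14 = 3,500 mg from Day 1 (28% and 16% of 22,400 mg). That is the weaker reading. The count table orders discontinuation at the lowest dose only above 400 or 15, and the footnote applies only if further reduction is required.

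**Length of a hold.** A reader might infer that a count-driven hold has no end, because the 14-day limit in 6.1.2.3 names only neutropenia, liver tests and diarrhea. But section 7.1 provides for withdrawal after more than 14 days of interruption for toxicity as defined in 6.1.2.3, without that list. Whether it reaches a count that was never low depends on whether such a count is a toxicity, and the text leaves that unclear.

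**Week 4.** A reader might infer a flat contradiction between escalation in 6.1.2.1 and step-down in 6.1.2.3. It arises only if 6.1.2.1 is read by enrolled lineage, which its wording does not state. For that reason both planned doses are shown above.

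**Absolute triggers elsewhere.** One dose-changing liver row is relative to entry ("Increase in AST/ALT by x3 from level at the time of enrollment but less than 3 x ULN"). The other liver rows that interrupt or discontinue drug, and the blood pressure and neutropenia rows, are absolute. So absolute triggers are usual in this section. The difference is that those describe abnormal states, whereas platelets of 250 in an anemia-only subject do not.

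**Conclusion.** The point holds as one about a stated rule that misfires for single-lineage subjects. A never-low platelet count of 200–400 or hemoglobin of 13–15 meets a step-down trigger without drug effect or toxicity. A count above 400 or 15 meets a stop trigger whose restart level requires a healthy count to fall.

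The size that follows from the text is dose: 41% to 59% of the escalated plan, or 54% to 79% of the unescalated plan, for the subject assumed above.

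A reader might go on to infer a loss of power. The documents do not support a figure: they give no lineage mix, no frequency of such counts and no dose-response relation. The stated power and type I error stand. Any loss of response would work against the drug and would not create a false positive. The rows should be amended, but the number of subjects affected is unknown and site discretion may reduce it.

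**What to change.** Add above the count table in 6.1.2.3:

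> The platelet 200–400 and Hb 13–15 step-down rows apply only when that count was below the row's lower limit at baseline (section 4) and has risen into the range on study drug. The platelet >400 and Hb >15 rows apply to all subjects whose baseline was at or below that limit; if baseline was already above it, the PI decides whether to hold. If baseline was at or above the restart level (150 or 13), drug may resume on return to the baseline level.

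Also word the week-4 thresholds in 6.1.2.1 by enrolled lineage. State that a count row that applies under this rule takes precedence over escalation in single-lineage subjects, with a PI decision in Evans subjects whose two counts point in opposite directions.

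Tying the rows to baseline rather than to lineage alone keeps them active for a real on-drug rise in the other lineage, such as platelets going from 60 to 390 in an anemia-only subject. It also avoids a mandatory stop for a trivial change from, say, 405 to 406.

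The cost is a wording amendment needing IRB approval. No visits or tests are added: baseline is already defined for both counts and the CBC is already scheduled every 2 weeks. The downside is less automatic dose reduction for subjects who enter with a normal or high count in the non-enrolled lineage. A baseline just under a limit could still cross it by ordinary variation.

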6.1.2.4 Drug Administration

Fostamatinib may be taken with or without food. In the case of a missed dose of fostamatinib subjects should take their next dose at its regularly scheduled time. For subjects able to swallow medication should be taken orally. For subjects who are unable to swallow, drug should be crushed and provided via feeding tube access. Tablets should be crushed until granular with an approximate particle size <2 mm, added to approximately 10 mL of water, and stirred to mix before administration through the orogastric or nasogastric tube.

Subject who are on a strong CYP3A4 inhibitor and unable to switch to a moderate or low CYP3A4 inhibitor, the starting dose for the 1st 4 weeks would be 150 mg daily and can be escalated to 100 mg BID if refractory cytopenias and able tolerate the treatment at the 4-week assessment visit. Subject who are on a weak or moderate CYP3A4 inhibitor can start at the routine dose of 100mg BID and follow closely for adverse events. See appendix A for a full list of CYP3A4 inhibitors.

6.2 PREPARATION/HANDLING/STORAGE/ACCOUNTABILITY

6.2.1 Acquisition and Accountability

Investigational product (IP) will be shipped to the site either directly from Rigel Pharmaceuticals, or from other regional or local drug repositories. All other supplies should be provided by the site. Multiple lots of IP may be supplied.

The site PI is responsible for study product distribution and disposition and has ultimate responsibility for study product accountability. The PI may delegate to the research pharmacist responsibility for study product accountability. The site's research pharmacist will be responsible for maintaining complete records and documentation of study product receipt, accountability, dispensation, storage conditions, and final disposition of the study product(s).

6.2.2 Formulation, Appearance, Packaging, and Labeling

Fostamatinib will be provided by Rigel Pharmaceuticals and stored in the pharmacy of each participating site. The drug product consists of 2 strengths of orange film-coated, plain, bioconvex tablets. The 150-mg tablet is oval and the 100-mg tablet is round. The tablets are supplied in white opaque high-density polyethylene bottles capped with white polypropylene child resistant closures with foil induction seals.

6.2.3 Product Storage and Stability

Store at room temperature, 20°C to 25°C (68°F to 77°F); excursions permitted between 15°C to 30°C (59°F to 86°F). Do not remove desiccants.

6.2.4 Preparation

For patients who are able to take oral medication there is no preparation of the tablets. For patients who are unable to take oral medication tablets should be crushed until granular with an approximate particle size <2 mm, added to approximately 10 mL of water, and stirred to mix before administration through the feeding tube.

Abbreviated Title: Fostamatinib for post-transplant cytopenias

Version Date: 11/28/2023

6.2.5 Return and Reconciliation

The number of tablets dispensed and returned is to be documented on the accountability log and reconciled by site personnel. The study monitor will review both the dispensing and dosing administration record to verify the drug accountability

6.2.6 IP Destruction

At the end of the trial all used and unused drug need to be destroyed by the site or designee. The CRA will complete the final accountability and ensure a Proof of Destruction is obtained.

Records of the destruction of any unused study drug must be kept and filed in the Pharmacy Binder and written confirmation must be provided to Rigel at the end of the trial to confirm destruction of surplus IP.

6.3 MEASURES TO MINIMIZE BIAS: RANDOMIZATION AND BLINDING

N/A

6.4 STUDY INTERVENTION COMPLIANCE

The research team will review the medication pill count upon follow up visits and document any missing doses.

6.5 CONCOMITANT THERAPY

For this protocol, a prescription medication is defined as a medication that can be prescribed only by a properly authorized/licensed clinician. Medications to be reported in the CRF are concomitant prescription medications used for the treatment of posttransplant cytopenias.

For patients that are eligible for the study, other therapy received prior to enrollment with any other experimental treatment or off-label use of marketed medications or currently stable dose for 15 days prior to enrollment is not an exclusion criterion of the trial.

Do not report vitamins, herbal supplements, or topical medications. Do not report over-the- counter medicines that the subject reportedly took at home prior to enrollment.

Please refer to section 2.3.1 for drug-drug interactions.

